EFFECTIVENESS OF DIABETES SELF-
MANAGEMENT EDUCATION ON GLYCAEMIC
CONTROL IN PATIENTS WITH TYPE 2 DIABETES
MELLITUS: A RANDOMISED CONTROLLED TRIAL

Principal Investigator

[name] [name]

Department of Medicine

Komfo Anokye Teaching Hospital

Supervisors

[name] [name]

[name] [name]

May 2023

Version 1 30 May 2023

LIST OF ACRONYMS

AADE- American Association of Diabetes Education

BMI- Body Mass Index

BP- Blood Pressure

DBP- Diastolic Blood Pressure

DM- Diabetes Mellitus

DSME- Diabetes Self- Management Education

FBG- Fasting Blood Glucose

HbA1c- Haemoglobin A1c

HDL-C- High Density Lipoprotein Cholesterol

KATH- Komfo Anokye Teaching Hospital

KNUST- Kwame Nkrumah University of Science and Technology

LDL-C- Low Density Lipoprotein Cholesterol

LMIC- Lower Middle-Income Country

M-health- Mobile health

MNT- Medical Nutrition Therapy

MODY- Maturity- Onset Diabetes of the Young

OPD- Outpatient Department

RCT- Randomised Control Trial

SBP- Systolic Blood Pressure

SGM- Self Glucose Monitoring

SPSS- Statistical Package for Social Sciences

SSA-Sub-Saharan Africa

Version 1 30 May 2023

T1DM- Type 1 Diabetes Mellitus

T2DM- Type 2 Diabetes Mellitus

TC- Total Cholesterol

TG- Triglycerides

WC- Waist circumference

WHO- World Health Organization

Version 1 30 May 2023

ABSTRACT

BACKGROUND: Diabetes mellitus prevalence has been rising rapidly in middle- and low-income countries. Diabetes self- management education (DSME) is a critical element of care for all people with diabetes and is necessary in order to improve patient outcomes. About 70% of patients with diabetes have poor glycaemic control in Ghana. This situation necessitates effective diabetes control measures including DSME, especially noting that a 1-point improvement of HbA1c is associated with a 20% and 30%-40% decrease in macrovascular and microvascular complications, respectively.

OBJECTIVES: To determine the effectiveness of diabetes self-management education on glycaemic control when combined with usual care vs usual care alone in patients with T2DM

METHODS: This is a parallel-group, 2-arm randomized controlled trial among sub-optimally controlled (HbA1c > 7.9%) T2DM patients to compare the effectiveness of a 6-month nurse led DSME intervention on glycaemic control in addition to usual diabetes care versus usual care alone.

ANALYSIS: Data will be analysed using the Statistical Package for Social Sciences (SPSS) Version 26 (SPSS Inc, Chicago, IL, USA) software program. Categorical variables will be displayed using frequencies and percentages. Continuous variables will be presented as means and standard deviations. Chi-square test of independence and student's t-test will be used to examine the association between any 2 categorical variables and 2 continuous variables respectively. The mean change in HbA1c after six months for all outcomes, will be calculated in both groups and the significance tested using the student's t-test for the mean difference between the intervention and control arm. Statistical significance for all tests will be set at the 0.05 level, and all analysis will be 2-tailed.

EXPECTED OUTCOME: Our study will evaluate the effectiveness of DSME in improving glycaemic control using a mixed delivery strategy. If DSME is shown to be effective it will enhance scaling up of this intervention in diabetes clinics and the adoption of this model in the

Version 1 30 May 2023

national diabetes management guidelines. This will lead to improved knowledge of diabetes, glycaemic control, reduced lost hours due to hospitalization from poorly controlled diabetes mellitus and improved patient outcomes.

BACKGROUND INFORMATION

2.1 INTRODUCTION

Diabetes mellitus (DM) prevalence has been rising rapidly in middle- and low-income countries. Africa is reported to have 24 million adults (20-79) living with DM in 2021, majority being Type 2 Diabetes Mellitus (T2DM). This figure is estimated to increase to 33 million by 2030 and 55 million by 2045. Diabetes was responsible for 416,000 deaths in 2021(1).

DM is a major cause of blindness, kidney failure, heart attacks, stroke and lower limb amputation(1). Almost half of all deaths attributable to high blood glucose occur before the age of 70 years. The World Health Organization (WHO) projects that diabetes will be the 7th leading cause of death in 2030 (1).

Healthcare in developing countries primarily focuses on acute disease, relying little on laboratory services, and offers limited patient follow-up. By contrast, chronic disease management requires sustainable laboratory services, training of the healthcare workforce, the availability of appropriate drugs, and patient education in nutrition and self-care (2).

Patients with T2DM need complex care to control acute complications and reduce their risk of long-term complications. Patients with T2DM require not only ongoing medical care, but also diabetes self-management, which patients must do themselves. Effective glycaemic control is a vital component of the management of patients with T2DM. A healthy lifestyle, appropriate diet, and medication adherence are essential factors for good glycaemic control (3).

The American Diabetes Association has recommended haemoglobin A1c (HbA1c) as the established standard measurement for assessing glycaemic control in individuals with diabetes. Following the guidelines, an HbA1c level of around 7% indicates good glycaemic control (4).

Recent studies have shown that a high proportion of patients attending the Diabetes Clinic in Ghana have poorly controlled diabetes and this has serious implications for the management of T2DM diabetes as it suggests that current hospital-based treatment measures are less effective(5). Hence, patients with diabetes need self-management education to assist them in comprehending and dealing with the disease.

Diabetes self-management education (DSME) is a critical element of care for all people with diabetes and is necessary in order to improve patient outcomes (6). DSME is the ongoing process of facilitating the knowledge, skill, and ability necessary for diabetes self-care. This process incorporates the needs, goals, and life experiences of the person with diabetes and is guided by evidence-based standards (6). The overall objectives of DSME are to support informed decision-making, self-care behaviours, problem-solving and active collaboration with the health care team and to improve clinical outcomes, health status, and quality of life (6). It improves glycaemic control which has been shown to reduce micro and macrovascular complications (7).

About 70% of patients with diabetes have poor glycaemic control in Ghana (8). This situation necessitates effective diabetes control measures including DSME, especially noting that a 1-point improvement of HbA1c is associated with a 20% and 30% – 40% decrease in macrovascular and microvascular complications, respectively (7). DSME has been shown to reduce HbA1c averagely by 0.76% immediately after follow-up, 0.26% after 1-3 months and 0.26% after 4 months and beyond (9). It has been shown by various studies that self-management in Sub-Saharan Africa (SSA) is poor and a serious threat to glycaemic control (10).

Diabetes care in lower middle-income countries (LMIC) is beset with gaps especially in the area of DSME leading to poor outcomes. A meta-analysis of DSME among African Americans showed that DSME leads to non-significant improvement in HbA1c (11). Systematic meta-analysis of DSME in SSA has shown that limited research has evaluated this practice with only two reported in Ghana using mobile phone intervention and structured group education respectively which showed reduction in mean HbA1c(5,12–14). The limited availability of evidence supporting the use of DSME in Ghana has led to difficulty in scaling up the use of this effective intervention across the country.

In Ghana, unstructured diabetes education is usually given on an ad hoc basis by nurses at hospital waiting areas and by physicians during consultation and we are yet to conduct a study that evaluates how DSME delivered via a mixed delivery strategy will improve glycaemic control.

Thus, the objective of this study is to evaluate the effectiveness of DSME when combined with usual care on glycaemic control as compared to usual care alone in patients with sub-optimal glycaemic control.

2.2 RESEARCH QUESTION

Does diabetes self-management education when combined with usual care improve glycaemic control when compared to usual care alone?

2.3 AIM AND OBJECTIVES

2.3.1 AIM

To determine the effectiveness of diabetes self-management education on glycaemic control when combined with usual care vs usual care alone in patients with T2DM.

2.3.2 SPECIFIC OBJECTIVES

- 1) To determine the effectiveness of the intervention on HbA1c
- 2) To determine the effectiveness of the intervention on Fasting blood glucose (FBG)
- 3) To determine the effectiveness of the intervention on Blood pressure (BP) control
- 4) To determine the effectiveness of the intervention on body weight
- 5) To determine the effectiveness of the intervention on Low density lipoprotein cholesterol (LDL-C)

2.4 HYPOTHESIS

Diabetes self-management education when combined with usual care vs usual care alone leads to reduction in HbA1c (improvement in glycaemic control) in patients with Type 2 DM.

2.5 OUTCOMES

2.5.1 PRIMARY OUTCOME

Mean change in HbA1c at 6 months

2.5.2 SECONDARY OUTCOMES

- 1) Mean change in FBG at 3 months
- 2) Mean change in blood pressure at 6 months
- 3) Mean change in body weight at 6 months
- 4) Mean change in LDL-C at 6 months

2.6 INCLUSION CRITERIA

- 1) Patients with T2DM who are at least 18 years old without any co-morbidities requiring immediate hospitalisation
- 2) HbA1c >7.9%
- 3) Have access to a personal mobile phone and able to answer calls
- 4) Mentally stable, with no vision, verbal, or hearing impairments
- 5) Must have access a glucometer
- 6) Consents to the study

2.7 EXCLUSION CRITERIA

- 1) Other forms of DM such as type 1 DM or gestational diabetes
- 2) End-stage renal disease(eGFR<15ml/min)
- 3) Anaemia
- 4) History of stroke with paresis

METHODOLOGY

3.1 STUDY SITE

The study will be conducted at the Diabetes Centre of Komfo Anokye Teaching Hospital (KATH) in Kumasi, the second largest urban area in Ghana. Kumasi has an estimated T2DM prevalence of 3.8% (15), which is higher than the national prevalence of 2% (16).

KATH is a 1200 bed capacity tertiary level health facility affiliated to KNUST and the most advanced healthcare facility in the city running an outpatient diabetes clinic. The clinic runs weekly with the exception of Thursdays and receives referrals for adults > 18 years with diabetes from 9 out of the 16 administrative regions of Ghana and serves an estimated population of 15 million (17). A quarter of referrals to the clinic are received from health centres located within the northern and middle belts of Ghana while the remainder are referred from within the teaching hospital particularly after patients have been discharged as inpatients. On average, 40 patients attend the clinic daily. The Diabetes Centre is manned by endocrinologists, diabetes specialist doctors and nurses, pharmacists and dieticians.

3.2 STUDY DESIGN

This is a parallel-group, 2-arm randomized controlled trial among sub-optimally controlled ($\text{HbA1c} > 7.9\%$) T2DM patients to compare the effectiveness of a 6-month DSME intervention on glycaemic control in addition to usual diabetes care with usual care alone.

The minimum sample size of study participants will be determined using the formula (18)

$$n_i = 2 \left(\frac{Z_{1-\alpha/2} + Z_{1-\beta}}{ES} \right)^2$$

$$ES = \underline{\mu_1 - \mu_2}$$

$$\sigma$$

Where n_i is the sample size in each of the groups for a statistically significant study;

$\mu_1 - \mu_2$ is the absolute value of the difference in means (HbA1c) between the two groups expected under the alternate hypothesis which is 1.5% for this study;

σ = standard deviation of the outcome of interest which is 2.25 based on study by Asante et al(14)

ES is effect size which is calculated to 0.7

$1 - \beta$ is the power which is 80% for this study and $Z_{1-\beta}$ is the value from the standard normal deviation holding $1 - \beta$ below it.

α is the selected level of significance which is 0.05 for this study, $Z_{1-\alpha/2}$ is the value from the standard normal deviation holding $1 - \alpha/2$ below it. selected level of confidence set at 0.05 for this study

32 subjects in each group will be needed to ensure an adequate trial. An assumed 15% attrition and drop-out rate over the study period will be added to make a total sample size of 74 participants.

[figure not shown]

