3.11 PLAN FOR DATA MANAGEMENT

3.11.1 STATISTICAL ANALYSIS

Data will be analysed using the Statistical Package for Social Sciences (SPSS) Version 26 (SPSS Inc, Chicago, IL, USA) software program. Categorical variables will be displayed using frequencies and percentages. Continuous variables will be presented as means and standard deviations. Chi-square test of independence and student's t-test will be used to examine the association between any 2 categorical variables and 2 continuous variables respectively.

The mean change in HbA1c after six months for all outcomes, will be calculated in both groups and the significance tested using the student's t-test for the mean difference between the intervention and control arm.

Statistical significance for all tests will be set at the 0.05 level, and all analysis will be 2-tailed.

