3.12.3 LIMITATIONS OF STUDY

The research is being conducted at a single tertiary hospital centre which may not reflect fully what is happening at the regional and district hospitals. Also, there is a high level of expertise in the tertiary hospital setting hence usual care of patients with T2DM may be comparable to a structured DSME.

Furthermore, this study has only a 6 month follow up period and it is therefore not clear how sustainable participant adherence and improvements in glycaemic control will be maintained over longer time period. Only individuals who have access to glucometers will be enrolled in the DSME intervention arm; this may lead to some degree of selection bias.

RELEVANCE OF STUDY

Diabetes mellitus is associated with significant morbidity, mortality and healthcare resource utilisation if poorly controlled. Patients with T2DM need complex care to control acute complications and reduce their risk of long-term complications. Patients with T2DM require not only ongoing medical care, but also diabetes self-management, which patients must do themselves. Effective glycaemic control is a vital component of the management of patients with T2DM.

The Ghana Standard Treatment Guideline recommends a glycaemic target of 7% which indicates good glycaemic control. However, about 70% of Ghanaian patients with Type 2 DM fail to reach glycaemic control targets due to the complex nature of type 2 diabetes self-management. Hence, patients with diabetes need self-management education to assist them in comprehending and dealing with the disease. Diabetes education about health behaviours, including diet, medication adherence, blood glucose self-monitoring, and physical activity, is essential for successful diabetes management.

Mixed delivery strategy structured DSME has not been adequately studied in Ghana considering the peculiarities of a resource poor healthcare system, availability of trained personnel and cultural set up.

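### The stated 80% power for a 1.5-point HbA1c difference comes from rounding the effect size 0.667 up to 0.7; at the planned size it is about 73% to 75%, and no source is shown for 1.5

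*Combined protocol and SAP*

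**What the plan says.** Section 3.2 uses the usual two-means formula, with n per group equal to twice the square of (z for alpha plus z for power) divided by the effect size. Its inputs are:

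- a difference "expected under the alternate hypothesis which is 1.5% for this study", with no reference or rationale attached;
- a "standard deviation of the outcome of interest which is 2.25", referenced to an earlier study;
- the statement that "ES is effect size which is calculated to 0.7";
- for 1 − β, that it "is the power which is 80% for this study";
- for alpha, that it "is the selected level of significance which is 0.05 for this study". Section 3.11.1 adds that "all analysis will be 2-tailed".

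The result is 32 per group, raised to 74 in total for an assumed 15% attrition.

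The primary outcome (2.5.1) is the mean change in HbA1c at 6 months, compared between arms by Student's t-test (3.11.1). The intervention lasts those same 6 months (3.7.2).

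On effect size, section 2.1 reports that "DSME has been shown to reduce HbA1c averagely by 0.76% immediately after follow-up, 0.26% after 1-3 months and 0.26% after 4 months and beyond". It also mentions a meta-analysis with a non-significant improvement and two Ghanaian studies that found a reduction, without giving its size. Section 3.12.3 warns that at this tertiary site "usual care of patients with T2DM may be comparable to a structured DSME".

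**The concern.** Two things in the sample-size paragraph do not fit together.

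First, the effect size is a ratio of two numbers given in the same paragraph, and that ratio is not 0.7. Rounding up an effect size always lowers the calculated sample size, so the 80% attached to 32 per group is not the power for the stated difference and SD.

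Second, the difference itself stands without support, while the only figure the protocol gives for the effect of such education at the end of the programme is about half as large.

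What is at stake is how the result is read. Section 3.11.1 commits to a significance test at 0.05 and does not mention a confidence interval. If the trial is reported as having 80% power and the test is not significant, nothing in the plan shows which effects remain compatible with the data.

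**Working it through.** **Inputs.** Difference 1.5, SD 2.25, effect size 0.7, power 80%, alpha 0.05, 32 per group, 15% attrition and total 74 (all from 3.2); two-sided testing and the t-test (3.11.1); equal allocation (3.8); comparator effect 0.76 (2.1).

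**1. Reproducing the plan's figure.** With z values 1.960 and 0.842:

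- n = 2 × (1.960 + 0.842)² / 0.7² = 32.04, stated as 32 (strict rounding up gives 33).
- 64 × 1.15 = 73.6, stated as 74, or 37 per arm.

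So the plan used 0.7. It also multiplied by 1.15 where dividing by 0.85 would give 76, a difference of only 2 participants.

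**2. The same formula with the unrounded ratio.**

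- 1.5 / 2.25 = 0.667.
- n = 2 × (1.960 + 0.842)² / 0.667² = 35.3, so 36 per group.

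Equivalently, an effect size of 0.7 at SD 2.25 is a difference of 0.7 × 2.25 = 1.575, not 1.5.

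**3. Power at the planned size.** The standard error of the difference is 2.25 × √(2/n). Power is from the noncentral t distribution with 2n − 2 degrees of freedom and noncentrality (difference / standard error). Expected completers are 74 × 0.85 = 62.9, about 31 per arm.

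| Analysed per arm | Standard error | Power at 1.5 | Power at 0.76 | Difference with 80% power | 95% CI half-width |
|---|---|---|---|---|---|
| 31 (after 15% loss) | 0.572 | 73% | 26% | 1.63 | 1.14 |
| 32 (stated requirement) | 0.563 | 75% | 26% | 1.60 | 1.12 |
| 37 (no loss) | 0.523 | 81% | 30% | 1.49 | 1.04 |

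The normal approximation gives 76% at 1.5 with 32 per arm, so the shortfall does not depend on using the t distribution.

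**4. Size of 1.5 against the protocol's own figure.** 1.5 / 0.76 = 1.97, about twice. With 31 per arm, an observed difference of exactly 0.76 would have a 95% interval of about 0.76 ± 1.14, or −0.4 to 1.9.

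**5. Sensitivity to the meaning of the SD.** The protocol does not say whether 2.25 is the SD of a single HbA1c value or of the change. If it is the former, the SD of change is 2.25 × √(2(1 − r)), where r is the baseline-to-6-month correlation. The range for r is an assumption. With 31 per arm:

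| r (assumed) | SD of change | Power at 1.5 | Power at 0.76 |
|---|---|---|---|
| 0.3 | 2.66 | 59% | 20% |
| 0.5 | 2.25 | 73% | 26% |
| 0.7 | 1.74 | 92% | 39% |

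Power at 1.5 passes 80% at a correlation of about 0.58.

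**The case against.** The strongest reply is that the shortfall is modest and conditional. With full follow-up, 37 per arm gives 81%. If 2.25 is the SD of a single value and the correlation exceeds about 0.58, the planned size is enough for 1.5. Both statements are correct. The first sets aside the plan's own 15% attrition; the second rests on an SD for change that the plan does not give. On the inputs as written, the 80% is not met.

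Four stronger readings may occur to a reader, and the documents do not support them:

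- **That the protocol's evidence contradicts 1.5.** It does not. Section 2.1 also cites Ghanaian studies without a magnitude, and 1.5 may come from one of them. The 0.76 is a general average, whereas this trial enrols only patients with HbA1c above 7.9% and adds two-weekly calls. The phrase "expected under the alternate hypothesis which is 1.5% for this study" is also ordinary wording for a design difference and need not be a forecast. What can be said is that no source is shown.
- **That 0.26 is the benchmark.** In 2.1 that figure belongs to later follow-up, while the primary outcome is measured at the end of the 6-month programme. The closer comparator is 0.76.
- **That the trial could not answer its question.** With a half-width of about 1.1, a result near zero would still exclude 1.5.
- **That a null result will be taken to show that the education does not work.** No section says so. The abstract speaks of scale-up only if effectiveness is shown, and 3.12.3 already warns of a small contrast with usual care.

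**Conclusion.** The sample-size statement is wrong as written. For a difference of 1.5 at SD 2.25 and two-sided 0.05, the planned size gives about 75% power with 32 analysed per arm and 73% with 31, against the stated 80%; the formula in 3.2 needs 36 per group. The cause is the rounding of 0.667 to 0.7. The shortfall of 5 to 7 percentage points rests on taking 2.25 as the SD of the analysed change and on the plan's own attrition rate.

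Separately, 1.5 is unsupported in the text, and for an effect of 0.76 power would be about 26% (20% to 39% over the assumed correlations). This calls for a rationale and a plain statement of power. It does not show that 1.5 is unattainable.

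**What to change.** No extra patients are needed. In 3.2:

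- correct the effect size to 0.667;
- say whether 2.25 is the SD of HbA1c level or of its change;
- give the source of 1.5, or the reason for choosing it as the difference to detect;
- replace the power statement with wording such as: with 74 randomised and 15% loss (about 31 per arm), SD 2.25 and two-sided 0.05, power is about 73% for a difference of 1.5, 80% for about 1.6, and 26% for 0.76.

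If 2.25 proves to be the SD of level, these percentages should be recalculated from an SD of change with its source.

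In 3.11.1, state that the primary result is the between-arm difference with its 95% confidence interval (expected half-width about 1.1 points), and that a non-significant result will be interpreted from that interval and not as evidence of no effect. A rule that the interval must exclude 0.76 before concluding lack of benefit is not recommended: 0.76 is a cited average, not a stated minimal important difference. With a half-width of 1.14, the observed difference would have to favour usual care by about 1.14 − 0.76 = 0.38 points to meet the rule.

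The change is to wording only. Its cost is that the stated power becomes less favourable.

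### The sample size uses an effect size of 0.7 where the stated inputs give 0.667; after the assumed 15% loss, 74 participants give about 75% power, not 80%

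*Combined protocol and SAP*

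**What the plan says.** The calculation is in section 3.2 (Study design) of the combined protocol and SAP. The effect size is defined there as the difference in means divided by the standard deviation. The stated inputs are:

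- difference in mean HbA1c: "expected under the alternate hypothesis which is 1.5% for this study"
- standard deviation: "standard deviation of the outcome of interest which is 2.25"
- effect size: "ES is effect size which is calculated to 0.7"
- power: "is the power which is 80% for this study"
- significance level: "is the selected level of significance which is 0.05 for this study"

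The section concludes that "32 subjects in each group will be needed to ensure an adequate trial" and continues: "An assumed 15% attrition and drop-out rate over the study period will be added to make a total sample size of 74 participants".

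Section 3.8 gives equal allocation. Section 3.11.1 makes all tests two-tailed and has the change in HbA1c compared between arms, with "the significance tested using the student's t-test for the mean difference between the intervention and control arm".

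The study budget allows for 148 lipid profiles, which is 74 × 2. This matches the baseline and 6-month blood draws in section 3.9.3 and indicates that 74 is the working target.

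**The concern.** The stated effect size does not follow from the two numbers printed just before it, and no other section gives a different difference, a different standard deviation or a reason for 0.7. The effect size is squared in the denominator of the formula, so rounding it up by 5% (0.7/0.667 = 1.05) cuts the required number by about 9% (1/1.05² = 0.907). The error is in the unsafe direction.

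80% is the only power figure in the plan, and a null result would be read against it. If true power is nearer 75%, the chance of missing a real 1.5-point difference is about one in four, not one in five.

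**Working it through.** **Inputs (section 3.2 unless noted).** Difference 1.5; SD 2.25; two-sided alpha 0.05 (z = 1.960); power 80% (z = 0.842); equal groups (section 3.8); 15% loss.

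**1. Reproduce the plan's figures.** The formula is n per group = 2 × ((1.960 + 0.842)/ES)².

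- With ES = 0.7: n = 32.04, or exactly 32.0 with z-values of 1.96 and 0.84. This is the stated 32.
- Attrition: 64 × 1.15 = 73.6, rounded up to 74. This is the stated total.

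So the rounded 0.7 was the value used in the calculation.

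**2. Use the stated inputs.**

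- ES = 1.5/2.25 = 0.667.
- n = 35.32, so 36 per group.
- Conversely, 0.7 × 2.25 = 1.575, so 32 per group is the size for a difference of 1.575, which the plan does not state.

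**3. Attrition step.** To have 64 left after losing 15%, enrolment must be 64/0.85 = 75.3, so 76 for equal groups. With 74 enrolled, 74 × 0.85 = 62.9 remain (31.45 per group), just under the 64 required.

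**4. Power for 1.5 points with SD 2.25.** By the protocol's normal formula, power = Φ(ES × √(n/2) − 1.960). At 31.45 per group this is Φ(2.644 − 1.960) = Φ(0.684) = 75.3%. The t-test column uses the noncentral t distribution.

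| Situation | n per group | Formula | t-test |
|---|---|---|---|
| 74 enrolled, 15% lost | 31.45 | 75.3% | about 74% |
| Stated number completing | 32 | 76.0% | 74.7% |
| 76 enrolled, 15% lost | 32.3 | 76.4% | 75.1% |
| 74 enrolled, 5% lost | 35.15 | 79.8% | 78.7% |
| 74 enrolled, none lost | 37 | 81.8% | 80.8% |

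**5. Where the shortfall comes from.**

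- Rounding: even if 32 per group complete, the formula gives 76.0%, so about 4 points are lost before any question of attrition.
- Attrition step: 76.4% with 76 enrolled against 75.3% with 74, about 1 point.
- Test: moving from the normal formula to the t-test accounts for about 1.3 points in the last column. At ES 0.7 and 32 per group, t-test power is 78.7% against 80.0% by the formula. This comes from neither slip.

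**6. What 74 participants can deliver.**

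- Power reaches 80% only if loss is at most 4.5% by the formula (1 − 35.32/37) or 1.9% by the t-test (1 − 36.31/37).
- With 15% lost, the difference detectable with 80% power by the formula is 2.802 × √(2/31.45) × 2.25 = 0.7065 × 2.25 = 1.59 points. By the t-test it is 0.7179 × 2.25 = 1.62 points.

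**7. Enrolment for 80% power at 1.5 points with 15% loss.**

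- Formula: 36 per group, 72/0.85 = 84.7, so 86 for equal groups.
- t-test: 37 per group, 74/0.85 = 87.1, so 88.

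**The case against.** The best reply is that this is rounding in plain view. To one decimal, 0.667 is 0.7, every input is printed, and the practical consequence is a detectable difference of 1.59 instead of 1.5, a gap of 0.09 HbA1c points. If nobody is lost, 74 participants exceed 80%. All of that is true. But the plan itself assumes 15% loss, and the allowance made for loss is almost wholly used up by the rounding.

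A second reply is that uncertainty about the standard deviation matters more. With 31.45 per group and a 1.5-point difference, the formula gives 84.5% power for an assumed SD of 2.0, 80.1% for 2.12, 75.3% for 2.25 and 66.3% for 2.5. An SD about 6% lower would remove the shortfall. The plan also does not say whether 2.25 is the SD of the change in HbA1c, which is the primary outcome. This stands as a caution: the restated power holds only for SD 2.25 and should say so. It does not rescue the 80%, which the plan derives from 2.25.

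Third, the attrition slip is minor. At ES 0.7, 31.45 per group would still give 79.3%, so it would not merit comment alone. Planning a t-test with a normal formula is also common practice. Both points are fair, and the conclusion rests on the formula figures.

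**Conclusion.** The concern holds. On the plan's own difference, SD, significance level, formula and assumed loss, 74 participants give 75.3% power, not 80%. The risk of missing a true 1.5-point difference is about 25% by the formula, or 26% by the planned t-test. Most of the gap comes from rounding the effect size before use, and about 1 point from the attrition step.

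The result depends on 15% being lost and on the SD being 2.25. The 15% rate itself is not questioned. Nothing here affects the treatment estimate, the choice of test or the type I error. It is a moderate error in a stated design figure and should be corrected.

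**What to change.** In section 3.2, give the effect size as 1.5/2.25 = 0.667, apply attrition as n/(1 − 0.15), and replace the power claim with what 74 participants deliver. Suggested text:

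> With 74 enrolled and 15% lost, and an SD of 2.25, power to detect a 1.5-point difference is about 75% by this formula (about 74% by t-test). The difference detectable with 80% power is about 1.6 points. With no loss, power for 1.5 points is about 82% (81% by t-test).

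This is sufficient. It costs only protocol wording and a less favourable stated power.

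If the sponsor prefers to keep 80% power for 1.5 points with 15% loss, the total becomes 86 by the formula (12 more participants) or 88 by the t-test (14 more).
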